## 2. Change History

| Version/Date | Change Log     |
|--------------|----------------|
| 1.0          | Created as new |
|              |                |

## 4. Purpose

The Statistical Analysis Plan (SAP) describes the statistical methods to be used during the reporting and analyses of data collected under Aclaris Therapeutics, Inc. (Aclaris) Protocol ATI-1777-AD-201.

## 5. Scope

The SAP outlines the following:

- Study Objectives
- Study Design
- Endpoints
- Applicable Study Definitions
- Statistical Methods

## 6. Introduction

This SAP should be read in conjunction with the study [protocol V2.0](#), 10SEP2020 and electronic case report form (eCRF) V1.1 27OCT 2020. Any further changes to the protocol or eCRF may necessitate updates to the SAP. Changes following approval of the first version SAP will be tracked in the SAP Change History.

Final approval of the SAP by the Aclaris and PRA statisticians will occur prior to database lock and unblinding study treatment.

### 6.1. Changes from Protocol

The sample size computation was changed from one based upon a two-sided hypothesis test to one based upon a one-sided hypothesis test in order to match the planned primary analysis. The missing continuous efficacy endpoints will be imputed using last observation carry forward (LOCF) for all the continuous efficacy endpoints instead only for the primary efficacy endpoint (Protocol [Section 9.4.9](#)). Baseline severity of atopic dermatitis (AD) (moderate versus severe) was added as a covariate in the models assessing the efficacy parameters.

## 7. Study Objectives

### 7.1. Primary Objectives

The primary objective of this study is to assess the preliminary clinical efficacy of ATI-1777 topical solution in adult patients with moderate or severe AD.

### 7.2. Secondary Objectives

The secondary objective of this study is to assess the safety, tolerability, and pharmacokinetics (PK) of ATI-1777 topical solution twice daily for 4 weeks in adult patients with moderate or severe AD.

## 8. Study Design

This is a first-in-human, randomized, double-blind, parallel-group, multicenter, vehicle-controlled study to evaluate the efficacy, safety, tolerability, and PK of ATI-1777 solution following twice-daily applications to target areas of patients with moderate or severe AD. All AD lesions in protocol allowed areas should be treated.

Patients will undergo screening evaluations to determine eligibility up to 30 days prior to randomization. Patients who meet all the inclusion/exclusion criteria will be randomized on Day 1 to active or vehicle treatment. Patients will apply study drug (ATI-1777 topical solution 2.0% w/w or vehicle) twice daily for 4 weeks with weekly study visits and will return 2 weeks after the last dose of study medication for a Post-treatment Follow-up (PTFU) Visit. Adverse event (AE) collection, physical examinations, clinical disease assessments (Eczema Area and Severity Index [EASI], Investigator's Global Assessment [IGA], AD body surface area [BSA], Peak Pruritus Numerical Rating Scale

[PP-NRS]), vital sign assessments, PK evaluations, ECG assessments, and clinical laboratory evaluations will be performed as detailed in the Schedule of Events in [Table 1](#).

All AD lesions in protocol allowed areas should be treated. The study will be conducted at approximately 15 sites in the United States (US).

The study will consist of a Screening Period of up to 30 days, a 4-week Treatment Period, and a 2-week PTFU period. The maximum total duration of the study for patients remaining in the study until their final follow-up assessment will be 73 days.

It is planned to enroll approximately 42 patients. Patients will be randomized (1:1 to ATI-1777 Topical Solution 2.0% w/w or vehicle) to achieve approximately 34 evaluable patients having a non-missing Week 4 EASI assessment.

## 8.1. Sentinel Dosing

A sentinel dosing strategy will be employed. A minimum of 4 and a maximum of 8 patients will be initially enrolled in the study. Study enrollment will then be paused until the initial 4 to 8 patients have completed their Day 8 Visit and safety data from these patients has been reviewed by the sponsor and the ProPharma safety physician to determine whether the study should continue or be stopped. If the safety data from the first 4 to 8 patients indicate that it is safe to continue the study, enrollment will be resumed.

The first 4 to 8 patients will continue in the study according to the Schedule of Events in Table 1 while the review of their safety data is ongoing and will continue in the study after enrollment resumes.

## 8.2. Stopping Rules

A patient will stop treatment with investigational agent if one or combination of the following occurs during the study:

- An infection which meets the criteria as a study medication-related serious adverse event (SAE)
- A deep venous thrombosis (DVT) and/or pulmonary embolism (PE)
- Lymphoma
- Hy's law ([Appendix 1](#))

Treatment with study medication should be temporarily interrupted in the event of severe AEs considered related to study medication, or in the event of one or more of the abnormal laboratory values in [Appendix 2](#).

[figure not shown]
The sponsor and ProPharma safety physician will meet regularly (every 4 weeks) and assess the ongoing safety of the study. Attention will be paid to the number of severe AEs and SAEs, with particular focus paid to the number of patients who meet individual patient stopping rules. PK data will be used in the assessment: events associated with high plasma levels will be considered of high significance.

If the study is stopped, a restart will not occur without agreement of the institutional review board (IRB) and the sponsor's medical monitor.

The study overview is specified in [Figure 1](#).

The schedule of study events is specified in Table 1.

**Figure 1 Study Schematic**

**Table 1 Schedule of Events**

| Study Period  | Screening | Treatment Period |                  |                   |                      | PTFU              |
|---|-----------|------------------|------------------|-------------------|----------------------|-------------------|
| Study Day   | -30 to -1 | Day 1            | Day 8
±3 days | Day 15
±3 days | Day 28/ET
±2 days | Day 42
±3 days |
| Informed Consent    | X         |                  |                  |                   |                      |                   |
| Inclusion/Exclusion criteria  | X         | X                |                  |                   |                      |                   |
| Demographics  | X         |                  |                  |                   |                      |                   |
| Medical history, including AD history   | X         | X                |                  |                   |                      |                   |
| Full physical examination   | X         |                  |                  |                   |                      |                   |
| Brief physical examination    |           | X                |                  |                   |                      | X                 |
| SARS-CoV-2 nasopharyngeal test  |           | X                |                  |                   |                      |                   |
| ECG   | X         |                  |                  |                   |                      | X                 |
| Vital signs   | X         | X                | X                | X                 | X                    | X                 |
| Serum pregnancy test    | X         |                  |                  |                   |                      |                   |
| Urine pregnancy test  |           | X                | X                | X                 | X                    |                   |
| Clinical chemistry, hematology, urinalysis                          | X         | X                | X                | X                 | X                    |                   |
| Virology (Hepatitis B and C, HIV)   | X         |                  |                  |                   |                      |                   |
| QuantiFERON® Tuberculosis Gold Test   | X         |                  |                  |                   |                      |                   |
| Randomization   |           | X                |                  |                   |                      |                   |
| PK sample   |           | X                | X                | X                 | X                    |                   |
| Fitzpatrick skin type assessment  | X         |                  |                  |                   |                      |                   |
| EASI    | X         | X                | X                | X                 | X                    |                   |
| IGA   | X         | X                | X                | X                 | X                    |                   |
| BSA   | X         | X                | X                | X                 | X                    |                   |
| PP-NRS    |           | X                | X                | X                 | X                    |                   |
| Photography   | X         | X                | X                | X                 | X                    |                   |
| Dispense study drug and patient diary   |           | X                | X                | X                 |                      |                   |
| Study drug instruction, first administration, and observation                   |           | X                |                  |                   |                      |                   |
| Study drug administration (by patient)                              |           | X                | X                | X                 | X                    |                   |
| Collection of study drug, patient diary review, including medication compliance |           |                  | X                | X                 | X                    |                   |
| AE assessment    | X         | X                | X                | X                 | X                    | X                 |
| Prior and concomitant medication review   | X         | X                | X                | X                 | X                    | X                 |

AD = atopic dermatitis; AE = adverse event; BSA = body surface area; EASI = Eczema Area and Severity Index; ECG = electrocardiogram; ET = Early Termination; HIV = human immunodeficiency virus; ICF = informed consent form; IGA = Investigator's Global Assessment; PK = pharmacokinetic; PP-NRS = Peak Pruritus Numerical Rating Scale; PTFU = Post-treatment Follow-up; SAE = serious adverse event; SARS-CoV-2 = severe acute respiratory syndrome coronavirus 2; WOCBP = women of child bearing potential

1. A written, signed ICF must be obtained from each patient prior to performing any study-related procedure.
2. A full examination will be performed at the Screening Visit. A full examination will include general appearance, skin, head, eyes, ears, nose, throat, neck, thyroid, chest/lungs, heart, abdomen, lymph nodes, and extremities. A brief examination will be performed at the Day 1 and Day28/ET Visits and any unscheduled visits and will include symptom-focused assessments.
3. Triplicate 12-lead ECGs will be obtained as outlined in [Section Error! Reference source not found..](#)
4. Vital signs will be measured in a semi-supine position after 5 minutes of rest and will include temperature, systolic and diastolic blood pressure, pulse, and respiratory rate. Height will be measured and recorded at the Screening Visit, and weight will be measured and recorded at each study visit.
5. Serum pregnancy test at the Screening Visit, urine pregnancy test at all other specified time points; for WOCBP only.
6. On dosing day(s), sampling for the analysis of clinical laboratory parameters will be performed before the administration of study medication.
7. PK samples will be drawn as outlined in [Section Error! Reference source not found..](#)
8. IGA and BSA assessed at the Screening Visit to ensure inclusion criteria are met. EASI, IGA, BSA, and PP-NRS assessed prior to study medication application on Day 1 to establish baseline and at study visits and end of the study (or ET) to document severity and extent of AD following study medication. The patient will complete the PP-NRS in their diary each morning before applying study medication during the Treatment Period.
9. Study medication will be applied at the site on study visit days, except Day 28 for PK subgroups 2 and 3. On Day 28, study medication will be applied at home to accommodate the timing of PK sample collection for PK subgroups 2 and 3.
10. Nonserious AEs will be collected after the patient's first application of study drug and continue until the patient's last visit. SAEs will be collected from the time the patient signs the ICF until the patient's last visit.

### 8.3. Sample Size Considerations

A total of approximately 42 patients will be enrolled and randomized in order to achieve 34 patients who complete the study. Data from 34 patients provides 95.6% power to detect a statistically significant difference between the treatment groups in the primary endpoint (percent change from baseline in EASI scores). This power calculation is based upon a 1-sided treatment contrast within 1-way ANOVA model and assumes group means of 65% and 20% for ATI-1777 and vehicle, respectively. The group means were based upon slightly more conservative estimates than were observed in a Phase 2 study of topical ruxolitinib in AD. (Kim et al 2020b) The variance for the percent change from baseline in EASI was assumed to be 38.3%. This variance assumption was based upon data observed in a pilot AD study for the topical compound ATI-502 (ATI-502-AD-201).

### 8.4. Randomization

At Visit 2, in the morning of Day 1, eligible patients will be randomly assigned in a 1:1 ratio via an interactive voice/web response system (IXRS) to ATI-1777 or vehicle treatment.

Enrolled patients will be allocated a unique patient number in a sequential order by trial site. Following randomization, Aclaris will provide all study medication in a packed and labelled kit, and the IXRS will identify the kit number to be dispensed to the patient at each relevant visit according to the treatment assigned in the randomization schedule.

## 9. Study Endpoints, Variables and Covariates

### 9.1. Endpoints

The table below lists the endpoints vs objectives for the study.

| Objectives  | Endpoints   |
|---|---|
| Primary   | 
Primary endpoint
 
Percent change from baseline in EASI score at Week 4.
  |
| Secondary   | 
Secondary efficacy endpoints
 
 
Percent change from baseline in EASI score at each study visit
 
Proportion of patients achieving an IGA score of 0 to 1 combined with an improvement of 2 or more points from baseline within 4 weeks of the start of treatment
 
Proportions of patients who achieve 50%, 75%, and 90% improvement in EASI score (EASI-50, EASI-75, and EASI-90, respectively) within 4 weeks of the start of treatment
 
Change from baseline in IGA score at each study visit
 
Change from baseline in BSA at each study visit
 
Change from baseline in PP-NRS score at each study visit
 
 |
| Pharmacokinetic   | Pharmacokinetic endpoints   |
| The secondary objective of this study is to assess the safety, tolerability, and pharmacokinetics (PK) of ATI-1777 topical solution twice daily for 4 | The PK endpoint is ATI-1777 concentration in plasma samples obtained using a sparse sampling approach.  |

|   |  |
|---|--|
| weeks in adult patients with moderate or severe AD.   |  |
| Safety  | Safety endpoints   |
| The secondary objective of this study is to assess the safety, tolerability, and pharmacokinetics (PK) of ATI-1777 topical solution twice daily for 4 weeks in adult patients with moderate or severe AD. | 
 
Incidence of treatment-emergent adverse event (TEAE) and SAEs, including incidence of adverse event of special interest (AESI) (e.g., application site reactions)
 
Laboratory values
 
Vital signs
 
Physical examination results
 
12-lead ECG results
 
 |

## 9.2. Population Sets

The following analysis sets are defined in accordance with the International Council for Harmonization (ICH)-E9 guidance.

### 9.2.1. Full Analysis Set (FAS)

All patients who have been randomized and administered at least one dose of study medication. The efficacy analyses will be conducted on the FAS population as randomized; the safety analyses and summaries will be conducted on the FAS as treated.

### 9.2.2. Per-Protocol (PP) Set

The Per-Protocol (PP) set is defined as a subset of the FAS who have non-missing Week 4 EASI scores recorded with no major protocol deviations deemed to compromise the assessment of efficacy. Major protocol deviations will be identified as a subset of the Important protocol deviations and fully defined prior to unblinding of the trial. The PP analysis will only be conducted on efficacy endpoints and patients analyzed according to their actual treatment.

### 9.2.3. Pharmacokinetic (PK) Analysis Set

All patients who have received at least 1 dose of active study medication and provided at least 1 plasma concentration value will be included in the PK Analysis Set.

## 9.3. Predetermined Covariates and Prognostic Factors

The following factors will be adjusted as covariates:

- Baseline severity of AD (moderate vs severe)
- Continuous baseline severity EASI score/BSA score/IGA score
- Baseline BSA (3 to 10 vs greater than 10 to 20) to be used for PK spaghetti plots

## 10. Conventions and Derivations

Patients who discontinue study medication will be asked to come to each visit for the scheduled assessments up to the end of the study.

Patients who prematurely discontinue the study will be evaluated based on the data collected at each visit attended. Data collected during the ET Visit will be used as an end-of-study assessment for these patients. If the ET Visit was performed >1 day after the last dose was administered, then the previous visit will be used as the end-of-study assessment.

### 10.1.1. Study day and Visit Window

For each patient there will be a baseline period, a four-week treatment period and a two-week post treatment follow up period.

Study day is defined relative to the date of the first dose of study drug. For assessments that occur after this visit date, study day is calculated as (assessment date – first dose date + 1). For assessments that occur prior to first dose date, study day will be calculated as (assessment date – first dose date). There is no study Day 0. When there are multiple observations within a visit window, the value closest to the target day will be analyzed.

The visit window ([Table 2](#)) and PK draw window ([Table 3](#)) appear in the table below.

Table 2 will be used to define the analysis window for safety assessments (vital signs, ECGs, lab assessment) and for efficacy assessment of EASI, IGA, BAS, PP-NRS). Plasma concentrations will be summarized according to nominal time (no analysis visit windows) and may be plotted according to actual time relative to the time of first dose, as appropriate.

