A total of approximately 50 patients who meet all the entry criteria will be randomized on Day 1 via an interactive voice/web response system (IXRS) to ATI-1777 or vehicle treatment in a 1:1 ratio. Patients will be stratified at randomization by severity of AD (moderate versus severe). The study is randomized and double-blinded with regard to ATI-1777 and vehicle in order to prevent bias in treatment allocation and in the assessment of treatment effect. The investigator, site personnel, the sponsor, and their representatives involved in monitoring and conducting the study, and the patients will be blinded to the study medication administered. See [Section 7.3](#) for further details on the

method of assigning patients to the treatment groups, and [Section 7.2](#) for details on access to the treatment codes in the event of emergency unblinding.

During the Treatment Period, patients will apply study drug (ATI-1777 topical solution 2.0% w/w or vehicle) twice daily for 28 days to target areas affected by AD. Patients will be trained by site personnel on how to appropriately apply the study medication. See [Section 7.4](#) for further details on the dose and administration of ATI-1777 and vehicle.

On Day 1 of the study, patients will apply drug in the clinic. The application site will be assessed for serious or severe local AEs prior to discharge from the clinic. Subjects will be informed to contact the site if a severe or serious event occurs. Subjects will be asked to pay particular attention to any events in the first 24 hours after drug administration.

During treatment, patients will attend weekly study visits. At the study visits, AE collection, physical examinations, clinical disease assessments (EASI, IGA, BSA, and PP-NRS), vital sign assessments, PK evaluations, and clinical laboratory evaluations will be performed as detailed in the Schedule of Events (Table 1). Patients will complete a daily diary recording their dose administration and PP-NRS itch score during the study.

For all study participants, blood samples will be collected for PK analysis according to the sparse sampling approach described in [Section 6.4](#).

Participants who discontinue study medication earlier than Day 28 will have an Early Termination (ET) Visit at the time of study medication discontinuation and will return for a PTFU Visit, 2 weeks (± 3 days) after the Day 28/ET Visit (see [Table 1](#)).

4.1.3 *Follow-up Period*

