**Table 2 Visit Window and Target day**

| Visit   | Target Study Day | Analysis Visit | Visit Window                           |
|---------|------------------|----------------|--|
| Visit 1 |                  | Screening      | < Time of First Dose                   |
| Visit 2 | 1                | Day 1          | Time of First Dose < Study Day ≤ Day 3 |
| Visit 3 | 8                | Day 8          | Day 4 < Study Day ≤ Day 11             |
| Visit 4 | 15               | Day 15         | Day 12 < Study Day ≤ Day 21            |
| Visit 5 | 28/ET            | Day 28/ET      | Day 22 < Study Day ≤ Day 34            |
| Visit 6 | 42               | Day 42         | Day 35 < Study Day ≤ Day 45            |

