### 12.6.3. Vital Signs

Vital signs will include blood pressure, heart rate, respiratory rate, and body temperature, and will be measured at Screening, Day 1, Day 8, Day 15 and Day28/ET. Patients will be resting for at least 5 minutes before taking vital signs.

Body weight will be measured and recorded at each study visit. Height will be measured at Screening visit.

Summaries by visit will include data from scheduled assessments, and all data will be reported according to the visit window. Vital sign results and corresponding change from study baseline values will be summarized at each scheduled visit using descriptive statistics by treatment group.

All vital sign, body weight, and height measurements will be presented in a data listing. The actual values and change from baseline values at each time point will be summarized for the FAS.

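### SAP Table 2 assigns visits by study day, so an early terminator's follow-up vital signs and weight can be summarised as Day 28/ET

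*SAP*

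**What the plan says.** **Windows.** SAP 10.1.1 states: "Study day is defined relative to the date of the first dose of study drug". On scope it says: "Table 2 will be used to define the analysis window for safety assessments (vital signs, ECGs, lab assessment"), and it adds the efficacy assessments. In Table 2 the Visit 5 row (target day 28/ET) has the window "Day 22 < Study Day ≤ Day 34", and the Visit 6 row (target day 42) has "Day 35 < Study Day ≤ Day 45". When several values share a window, "the value closest to the target day will be analyzed". No term refers to the last dose, the ET date or the type of visit.

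**Reporting.** SAP 12.6.3 says of vital signs: "Summaries by visit will include data from scheduled assessments, and all data will be reported according to the visit window".

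**Timing of ET and PTFU.** Under Protocol 4.1.2, patients who stop medication before Day 28 "will have an Early Termination (ET) Visit at the time of study medication discontinuation and will return for a PTFU Visit". Sections 4.1.2 and 4.1.3 set PTFU 2 weeks (±3 days) after the Day 28/ET visit. Section 5.4.2 gives approximately 14 days after ET for patients who leave the study.

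**What is measured at PTFU.** SAP Table 1 marks vital signs in the PTFU column, and weight is taken at every study visit. Laboratory tests, EASI, IGA, BSA and PP-NRS are blank there. The ECG row carries a mark under PTFU, whereas SAP 12.6.5 lists only Screening and Day 28/ET. The visit list in SAP 12.6.3 leaves PTFU out for vital signs.

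**The concern.** Table 2 fits a patient who completes treatment: follow-up falls near Day 42 and has its own row. It does not fit a patient whose follow-up clock starts at an earlier ET visit. That patient's PTFU values can be filed under a treatment-period visit, while the ET values, taken when drug was stopped, are filed elsewhere or nowhere.

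At stake is the meaning of the Day 28/ET row for vital signs and weight in a first-in-human study with safety and tolerability as secondary objectives. A value from the follow-up visit would sit beside completers' end-of-treatment values with nothing to mark the difference. SAP Section 10 does attend to time since last dose for the ET visit: an ET visit more than 1 day after the last dose is not used as the end-of-study assessment. It has no matching rule for PTFU.

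**Working it through.** **Inputs.** Table 2 windows as printed, on whole study days: Day 8 = 5 to 11; Day 15 = 13 to 21; Day 28/ET = 23 to 34; Day 42 = 36 to 45. Days 4, 12, 22 and 35 belong to no window. PTFU day = ET day + 14, with a tolerance of 3 days either way (Protocol 4.1.2 and 4.1.3).

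**The plan's own case.** A completer has 28 + 14 = Day 42, which lies in the Day 42 window. The plan's figure reproduces.

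**Early terminators, PTFU at exactly + 14 days.**

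| ET day | Window of the ET value by day count | PTFU day | Window of the PTFU value |
|---|---|---|---|
| 2 to 7 | Day 1 (2–3), none (4), Day 8 (5–7) | 16 to 21 | Day 15 |
| 8 | Day 8 | 22 | none |
| 9 to 20 | Day 8 (9–11), none (12), Day 15 (13–20) | 23 to 34 | Day 28/ET |
| 21 | Day 15 | 35 | none |
| 22 to 26 | none (22), Day 28/ET (23–26) | 36 to 40 | Day 42 |

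For example, with ET on Day 14 the ET vital signs go to the Day 15 row. The PTFU vital signs on 14 + 14 = Day 28 go to the Day 28/ET row.

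**With the ±3-day tolerance.**
- PTFU always lands in Day 28/ET if ET + 11 ≥ 23 and ET + 17 ≤ 34, that is, ET on Days 12 to 17.
- It can land there if ET + 17 ≥ 23 and ET + 11 ≤ 34, that is, ET on Days 6 to 23.

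**Does the closest-to-target rule prevent it?** Suppose the ET value is also placed in Day 28/ET because of the label, and the target is Day 28. For ET on Days 9 to 20 the PTFU value is |ET + 14 − 28| = 0 to 6 days from target, and the ET value is 28 − ET = 8 to 19 days from it. The PTFU value is closer for every one of these ET days and is the one kept.

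**Number of patients.** The documents give no distribution of ET days. The planned shortfall is 50 − 34 = 16 patients in the protocol and 42 − 34 = 8 in the SAP. It says nothing about when these patients stop or whether they attend PTFU, so no count follows.

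**The case against.** **The 28/ET label.** Table 2 gives Visit 5 the target 28/ET, and SAP Section 10 uses ET data as the end-of-study assessment. If the ET date itself is the target for an early terminator, the ET value is closest and PTFU does not displace it. That reading is possible, but no rule states it, and an ET on Days 9 to 20 lies outside the printed window. The text is unclear at best.

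**Patients who keep attending.** Protocol 5.4.1 and 9.4.9 and SAP Section 10 provide for patients who stop drug to keep attending scheduled visits. Such a patient has a real Day 28 visit that is off drug by design. This stands: the problem concerns only patients who go from ET straight to PTFU. Protocol 4.1.2 describes that route for stopping drug early and 5.4.2 for leaving the study. The two sets of provisions do not fit together.

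**Little data is involved.** This also stands. Laboratory tests and efficacy scores are not scheduled at PTFU. If the visit list in SAP 12.6.3 governs, vital signs are not scheduled there either, and weight remains. All vital signs and weights are listed, and SAP 12.6 plans no formal statistics for safety.

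**Stronger readings.** A reader might infer that on-treatment QTcF results, including outlier counts, are diluted. The documents do not support this. The ECG mark at PTFU is contradicted by SAP 12.6.5. The brief-examination row of the same table shows a similar PTFU mark where its footnote and SAP 12.6.4 say Day 28, so both marks may be misplaced. Nor does the SAP call the Day 28/ET row on-treatment.

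**Conclusion.** The mismatch is real but narrow. As printed, Table 2 places PTFU vital signs and weight in the Day 28/ET summary for patients with ET on Days 9 to 20 who go straight to PTFU at + 14 days. For other ET days it places them in the Day 15 window, in Day 42, or in no window. This rests on three assumptions: windows are applied by literal day count; the patient follows the ET-then-PTFU route; and vital signs are taken at PTFU as SAP Table 1 shows.

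The consequence is mislabelled values in descriptive by-visit tables. It should not be read as touching the primary analysis, as affecting every early terminator, or as biasing the Day 28 results by some stated percentage. Any such percentage would need an assumed spread of ET days, which the documents do not give.

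**What to change.** 1. In SAP 10.1.1 and Table 2, assign every assessment from the PTFU visit to Day 42/PTFU by visit type, whatever its study day.
2. State that ET-visit values map to Day 28/ET in the safety summaries, and which value is used if a patient has both an ET and a Day 28 visit. Cover EASI in a separate sentence, because Table 2 also serves efficacy and the Per-Protocol set depends on a non-missing Week 4 EASI.
3. Reconcile SAP Table 1 with SAP 12.6.3 and 12.6.5 on whether vital signs and ECG are taken at PTFU.
4. Reconcile Protocol 4.1.2 with Protocol 5.4.1 and 9.4.9 and SAP Section 10 on whether patients who stop drug go to ET and then PTFU or keep attending scheduled visits.

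A cut-off based on the last dose is not needed. It would remove the off-drug Day 28 values of patients who are asked to keep attending.

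Items 1 to 3 cost a few sentences of SAP text and programming by visit type, with no new data. Item 4 may need a protocol clarification.
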